8.1 Administrative and General Procedures

8.1.1 Informed Consent

The investigator or medically qualified designee (consistent with local requirements) must obtain documented consent from each potential participant prior to participating in a clinical study or future biomedical research. If there are changes to the participant’s status during the study (eg, health or age of majority requirements), the investigator or medically qualified designee must ensure the appropriate consent is in place.

8.1.1.1 General Informed Consent

Consent must be documented by the participant’s dated signature on a consent form along with the dated signature of the person conducting the consent discussion.

A copy of the signed and dated consent form should be given to the participant before participation in the study.

The initial ICF, any subsequent revised written ICF, and any written information provided to the participant must receive the Institutional Review Board/Independent Ethics Committee's (IRB/IEC's) approval/favorable opinion in advance of use. The participant should be informed in a timely manner if new information becomes available that may be relevant to the participant's willingness to continue participation in the study. The communication of this information will be provided and documented via a revised consent form or addendum to the original consent form that captures the participant's dated signature.

Specifics about a study and the study population will be added to the consent form template at the protocol level.

The informed consent will adhere to IRB/IEC requirements, applicable laws and regulations, and Sponsor requirements.

8.1.1.2 Consent and Collection of Specimens for Future Biomedical Research

The investigator or medically qualified designee will explain the future biomedical research consent to the participant, answer all of his/her questions, and obtain written informed consent before performing any procedure related to the future biomedical research substudy. A copy of the informed consent will be given to the participant.

8.1.2 Inclusion/Exclusion Criteria

All inclusion and exclusion criteria will be reviewed by the investigator, who is a qualified physician, to ensure that the participant qualifies for the study.

8.1.3 Participant Identification Card

All participants will be given a participant identification card identifying them as participants in a research study. The card will contain study site contact information (including direct telephone numbers) to be used in the event of an emergency. The investigator or qualified designee will provide the participant with a participant identification card immediately after the participant provides written informed consent. At the time of intervention allocation/randomization, site personnel will add the treatment/randomization number to the participant identification card.

The participant identification card also contains contact information for the emergency unblinding call center so that a healthcare provider can obtain information about study intervention in emergency situations where the investigator is not available.

8.1.4 Medical History

A medical history will be obtained by the investigator or qualified designee before vaccination at Visit 1 (Day 1). The participant's relevant medical history for the 5 years prior to Visit 1 (Day 1) will be obtained to ensure that the participant satisfies the inclusion and exclusion criteria of the study. History of tobacco use will also be collected.

8.1.5 Prior and Concomitant Medications Review

8.1.5.1 Prior Medications

The investigator or qualified designee will review prior medication use, including any protocol-specified washout requirement, and record prior medication taken by the participant within 30 days before the study vaccination at Visit 1 (Day 1).

8.1.5.2 Concomitant Medications

The investigator or qualified designee will record medication, if any, taken by the participant during the study.

New and/or concomitant medications taken after Visit 1 (Day 1) and non-study vaccines received since Visit 1 will be recorded with the eVRC as specified in Section 8.3.4.

8.1.6 Assignment of Screening Number

All consented participants will be given a unique screening number that will be used to identify the participant for all procedures that occur prior to randomization. Each participant will be assigned only 1 screening number. Screening numbers must not be re-used for different participants.

8.1.7 Assignment of Treatment/Randomization Number

All eligible participants will be randomly allocated and will receive a treatment/randomization number. The treatment/randomization number identifies the participant for all procedures occurring after treatment allocation/randomization. Once a treatment/randomization number is assigned to a participant, it can never be re-assigned to another participant.

A single participant cannot be assigned more than 1 treatment/randomization number.

8.1.8 Study Intervention Administration

Unblinded study personnel not otherwise involved in the conduct of the study will prepare and administer V114 or Prevnar 13™. Study vaccines should be prepared and administered by appropriately qualified members of the study personnel (eg, physician, nurse, physician's assistant, nurse practitioner, pharmacist, or medical assistant) as allowed by local/state, country, and institutional guidance. Procedures for handling, preparing, and administering the unblinded vaccines are provided in the Investigator Trial File Binder. Unblinded study personnel should follow the preparation and administration instructions for Prevnar 13™ as specified in the product label.

Study vaccines should be removed from the refrigerator no more than 1 hour before vaccination. The time of removal and time of vaccination should be documented in the participant's chart.

Prior to administration of V114, the unblinded pharmacist should shake the product vigorously to obtain a homogenous white suspension. If white-colored insoluble particle appears, the unblinded pharmacist should use rapid, horizontal hand shaking for 5 to 10 seconds while holding the syringe in between the thumb and index finger until complete resuspension. This action should be repeated, as necessary. If appearance is otherwise, the vaccine should not be administered. The vaccine should not be used if the vaccine cannot be resuspended.

Study vaccine will be administered as a single 0.5-mL intramuscular injection, preferably in the deltoid region of the participant's arm. Adequate treatment provision, including epinephrine and equipment for maintaining an airway, should be available for immediate use should an anaphylactic or anaphylactoid reaction occur [Centers for Disease Control and Prevention 2015].

Unblinded study personnel should not have contact with participants for any study-related procedures/assessments after administration of study vaccines, which includes all safety follow-up procedures. All safety and immunogenicity assessments will be conducted by blinded personnel, and the participant will be blinded to the study vaccine received. Vaccination information, such as Component Identification Number and time of vaccination, must be recorded on the appropriate electronic Case Report Form (eCRF) as per the Data Entry Guidelines.

8.1.8.1 Timing of Dose Administration

Vaccinations may be administered at any time of day and without regard to timing of meals.

Each participant's body temperature must be taken before vaccine administration. Individuals who present with fever (oral or tympanic temperature $\geq 100.4^{\circ}\text{F}$ [$\geq 38.0^{\circ}\text{C}$] or axillary or temporal temperature $\geq 99.4^{\circ}\text{F}$ [$\geq 37.4^{\circ}\text{C}$]) will have the vaccination delayed until fever is resolved for at least 72 hours.

The collection of blood samples and administration of pregnancy tests (if applicable) must be done before each vaccine administration.

All participants will be observed for at least 30 minutes after vaccination for any immediate reactions. This observation must be performed by blinded site personnel for all study vaccines (Section 1.3 and Section 6.3.3).

8.1.9 Electronic Vaccination Report Card (eVRC)

The eVRC was developed to be administered electronically via a hand-held device. This item was structured as recommended in the final Food and Drug Administration Patient-Reported Outcome Guidance [U.S. Food and Drug Administration 2009]. The investigator or delegate will train the participant in the use of the eVRC at Visit 1 (Day 1).

Temperatures, injection-site reactions, vaccine-specific complaints, other complaints or illnesses, and concomitant medications or vaccinations will be recorded on the eVRC as

described in Section 1.3 and Section 8.3.4. The investigator or delegate will review the data captured on the eVRC with the participant at the Telephone Contact (Day 15) and Visit 2 (Day 30).

Any differences between eVRC data and the clinical database must be clearly explained in the participant's source documentation.

For the specific AEs collected via the eVRC, the investigator will use the information provided by the participant both on the eVRC and verbally at the time of eVRC review to apply the appropriate assessment of intensity and toxicity as described in Appendix 3.

8.1.10 Telephone Contact Questionnaire

Site personnel will contact the participant approximately 6 months after the last dose of study vaccine to collect additional information based on a Telephone Contact Questionnaire provided by the Sponsor. Data to be reported from this discussion will include SAEs and/or any updates to previously reported safety information.

8.1.11 Discontinuation and Withdrawal

Participants who receive a single-dose intervention cannot discontinue study intervention (see Section 7.1).

When a participant withdraws from participation in the study, all applicable activities scheduled for the final study visit (Visit 2) should be performed (at the time of withdrawal). Any AEs that are present at the time of withdrawal should be followed in accordance with the safety requirements outlined in Section 8.4.

8.1.11.1 Withdrawal From Future Biomedical Research

Participants may withdraw their consent for future biomedical research. Participants may withdraw consent at any time by contacting the investigator for the main study. If medical records for the main study are still available, the investigator will contact the Sponsor using the designated mailbox ([contact]). Subsequently, the participant's consent for future biomedical research will be withdrawn. A letter will be sent from the Sponsor to the investigator confirming the withdrawal. It is the responsibility of the investigator to inform the participant of completion of withdrawal. Any analyses in progress at the time of request for withdrawal or already performed prior to the request being received by the Sponsor will continue to be used as part of the overall research study data and results. No new analyses would be generated after the request is received.

In the event that the medical records for the main study are no longer available (eg, if the investigator is no longer required by regulatory authorities to retain the main study records) or the specimens have been completely anonymized, there will no longer be a link between the participant's personal information and their specimens. In this situation, the request for specimen withdrawal cannot be processed.

8.1.12 Participant Blinding/Unblinding

STUDY INTERVENTION IDENTIFICATION INFORMATION IS TO BE UNMASKED ONLY IF NECESSARY FOR THE WELFARE OF THE PARTICIPANT. EVERY EFFORT SHOULD BE MADE NOT TO UNBLIND.

For emergency situations where the investigator or medically qualified designee (consistent with local requirements) needs to identify the intervention used by a participant and/or the dosage administered, he/she will contact the emergency unblinding call center by telephone and make a request for emergency unblinding. As requested by the investigator or medically qualified designee, the emergency unblinding call center will provide the information to him/her promptly and report unblinding to the Sponsor. Prior to contacting the emergency unblinding call center to request unblinding of a participant's intervention assignment, the investigator who is a qualified physician should make reasonable attempts to enter the intensity/toxicity grade of the AEs observed, the relation to study intervention, the reason thereof, etc., in the medical chart. If it is not possible to record this assessment in the chart prior to the unblinding, the unblinding should not be delayed.

In the event that unblinding has occurred, the circumstances around the unblinding (eg, date, reason, and person performing the unblinding) must be documented promptly, and the Sponsor Clinical Director notified as soon as possible.

Once an emergency unblinding has taken place, the investigator, site personnel, and Sponsor personnel may be unblinded so that the appropriate follow-up medical care can be provided to the participant.

Participants whose treatment assignment has been unblinded by the investigator or medically qualified designee and/or nonstudy treating physician must be discontinued from study intervention, but should continue to be monitored in the study.

Additionally, the investigator or medically qualified designee must go into the IRT system and perform the unblind in the IRT system to update drug disposition. In the event that the emergency unblinding call center is not available for a given site in this study, the IRT system should be used for emergency unblinding in the event that this is required for participant safety.

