3 HYPOTHESES, OBJECTIVES, AND ENDPOINTS

Hypotheses are aligned with objectives in the Objectives and Endpoints table.

In healthy adults ≥ 50 years of age enrolled in the study:

Objectives	Endpoints
Primary	

• Objective: To evaluate the safety and tolerability of V114 with respect to the proportion of participants with adverse events (AEs).	
• Solicited injection-site AEs from Day 1 through Day 5 postvaccination• Solicited systemic AEs from Day 1 through Day 14 postvaccination• Vaccine-related serious adverse events (SAEs) from Day 1 to Month 6 postvaccination

Objectives	Endpoints

 • Objective: To compare the serotype-specific opsonophagocytic activity (OPA) geometric mean titers (GMTs) at 30 days postvaccination (Day 30) across 3 different lots of V114. 
Hypothesis: All 3 lots of V114 are equivalent as measured by the serotype-specific OPA GMTs for 15 serotypes in V114 at 30 days postvaccination.
 
(The statistical criterion for equivalence requires the bounds of the 95% confidence interval [CI] of the GMT ratio for each pairwise V114 lot-to-lot comparison of the OPA GMT ratio to be within 0.5 to 2.0)
	
 • Serotype-specific OPA responses for the 15 serotypes in V114 at Day 30

Secondary
	

 • Objective: To evaluate the serotype-specific Immunoglobulin G (IgG) geometric mean concentrations (GMCs) at 30 days post vaccination (Day 30) compared across the 3 different lots of V114 and combined lots of V114 compared to Prevnar 13™. 	
 • Serotype-specific IgG responses for the 15 serotypes in V114 at Day 30

 • Objective: To evaluate the serotype-specific geometric mean fold rises (GMFRs) and proportions of participants with a ≥ 4-fold rise from prevaccination (Day 1) to 30 days postvaccination (Day 30) for both OPA and IgG responses separately across 3 different lots of V114. 	
 • Serotype-specific OPA and IgG responses for the 15 serotypes in V114 at Day 1 and Day 30

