8.4 Adverse Events (AEs), Serious Adverse Events (SAEs), and Other Reportable Safety Events

The definitions of an AE or SAE, as well as the method of recording, evaluating, and assessing causality of AE and SAE and the procedures for completing and transmitting AE, SAE, and other reportable safety event reports can be found in Appendix 3.

Adverse events, SAEs, and other reportable safety events will be reported by the participant (or, when appropriate, by a caregiver, surrogate, or the participant's legally authorized representative).

The investigator and any designees are responsible for detecting, documenting, and reporting events that meet the definition of an AE or SAE as well as other reportable safety events. Investigators remain responsible for following up AEs, SAEs, and other reportable safety events for outcome according to Section 8.4.3.

The investigator, who is a qualified physician, will assess events that meet the definition of an AE or SAE as well as other reportable safety events with respect to seriousness, intensity/toxicity and causality.

8.4.1 Time Period and Frequency for Collecting AE, SAE, and Other Reportable Safety Event Information

All AEs, SAEs, and other reportable safety events that occur after the consent form is signed but before allocation/randomization must be reported by the investigator if they cause the participant to be excluded from the study, or are the result of a protocol-specified intervention, including but not limited to washout or discontinuation of usual therapy, diet, placebo treatment, or a procedure.

All AEs, SAEs, and other reportable safety events must be reported by the investigator from the day of allocation/randomization to the first vaccination and from the day of each vaccination through 14 days postvaccination. SAEs must also be reported throughout the duration of the individual's participation in the study, regardless of whether or not related to the Sponsor's product.

Additionally, any SAE brought to the attention of an investigator at any time outside of the time period specified in the previous paragraph also must be reported immediately to the Sponsor if the event is either:

1. A death that occurs prior to the participant completing the study.

OR

2. An SAE that is considered by an investigator who is a qualified physician to be vaccine-related.

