- The assessment of relationship will be reported on the CRFs/worksheets by an investigator who is a qualified physician according to his/her best clinical judgment, including consideration of the above elements.
- Use the following scale of criteria as guidance (not all criteria must be present to be indicative of a Sponsor's product relationship).
 - Yes, there is a reasonable possibility of Sponsor's product relationship:
 - There is evidence of exposure to the Sponsor's product. The temporal sequence of the AE onset relative to the administration of the Sponsor's product is reasonable. The AE is more likely explained by the Sponsor's product than by another cause.
 - No, there is not a reasonable possibility of Sponsor's product relationship:
 - Participant did not receive the Sponsor's product OR temporal sequence of the AE onset relative to administration of the Sponsor's product is not reasonable OR the AE is more likely explained by another cause than the Sponsor's product. (Also entered for a participant with overdose without an associated AE.)
- For each AE/SAE, the investigator must document in the medical notes that he/she has reviewed the AE/SAE and has provided an assessment of causality.
- There may be situations in which an SAE has occurred and the investigator has minimal information to include in the initial report to the Sponsor. However, it is very important that the investigator always make an assessment of causality for every event before the initial transmission of the SAE data to the Sponsor.
- The investigator may change his/her opinion of causality in light of follow-up information and send an SAE follow-up report with the updated causality assessment.
- The causality assessment is 1 of the criteria used when determining regulatory reporting requirements.

Follow-up of AE and SAE

- The investigator is obligated to perform or arrange for the conduct of supplemental measurements and/or evaluations as medically indicated or as requested by Sponsor to elucidate the nature and/or causality of the AE or SAE as fully as possible. This may include additional laboratory tests or investigations, histopathological examinations, or consultation with other health care professionals.
- New or updated information will be recorded in the CRF.

- The investigator will submit any updated SAE data to the Sponsor within 24 hours of receipt of the information.

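### The IRT disposition step in Section 8.1.12 can needlessly unblind the person who judges SAE causality: low weight, cheap to close

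*Combined protocol and SAP*

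**What the plan says.** Vaccine-related SAE is one of three primary safety endpoints. Section 3 lists it as "Vaccine-related serious adverse events (SAEs) from Day 1 to Month 6 postvaccination". Whether an SAE counts depends on a physician investigator, who under Section 8.4 assesses events "as well as other reportable safety events with respect to seriousness, intensity/toxicity and causality".

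Section 8.1.12 opens by limiting unmasking to what the participant's welfare requires. It asks the investigator to make reasonable attempts to chart the toxicity grade and relatedness before contacting the call center, and it says that unblinding must not wait if this cannot be done. It continues: "Once an emergency unblinding has taken place, the investigator, site personnel, and Sponsor personnel may be unblinded", with follow-up medical care as the reason. It then states that participants whose assignment was "unblinded by the investigator or medically qualified designee and/or nonstudy treating physician must be discontinued from study intervention". The next paragraph, opening with a word of addition, states that "the investigator or medically qualified designee must go into the IRT system and perform the unblind in the IRT system to update drug disposition".

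The outside route comes from Section 8.1.3. The participant card carries the call-center details "so that a healthcare provider can obtain information about study intervention in emergency situations where the investigator is not available".

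On later revision, Section 10.3.4 says: "The investigator may change his/her opinion of causality in light of follow-up information and send an SAE follow-up report with the updated causality assessment". It does not distinguish changes made before unblinding from changes made after it. Sections 9.4.2 and 9.6.2 do not say which causality assessment is analysed.

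**The concern.** Relatedness is a judgement. One of the elements that Section 10.3.4 asks the investigator to weigh is whether the event fits what is already known of the product. Knowing whether the participant received an investigational or a licensed vaccine can therefore feed straight into the answer. Section 4.2.2 justifies the comparator by the unbiased safety assessment it allows.

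When an outside provider breaks the blind, the investigator need not learn the arm unless the participant's care calls for it. The IRT sentence adds a second, mandatory code opening for a record-keeping purpose, and it can be read as covering this route. In a single-dose study nothing further will be dispensed to that participant. If the person who opens the code is also the person who judges causality, the study loses a blinded assessment of a serious event and gains nothing for the participant.

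**Working it through.** **1. The passages side by side.**

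- *Purpose.* The opening of 8.1.12 allows unmasking for participant welfare only. Its IRT sentence requires an unblind for drug disposition. These are different purposes, and the section does not reconcile them.
- *Who assesses.* Section 8.1.8 says that safety assessments are made by blinded personnel. Section 8.1.12 directs the investigator or a medically qualified designee to the IRT and does not exclude the person who judges causality.
- *What the IRT shows.* Section 6.8 describes the IRT as able to unmask identity, for the case where the call center is unavailable. What a later disposition update displays is not stated.
- *Reach to outside code breaks.* The IRT requirement follows directly after the sentence naming the nonstudy treating physician and makes no exception for that route. This is an inference from the order of the sentences.
- *Causality first.* The charting step is tied to contacting the call center. No matching step is given for a blind that someone else has already broken.
- *Origin.* The discontinuation order in 8.1.12 conflicts with Section 7.1, under which a single-dose intervention cannot be discontinued once given. The two passages must be reconciled. The mismatch suggests wording carried over from a multi-dose setting.

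**2. The plan's own SAE figures (Section 9.9.2, n = 2000 V114).** They concern any SAE, not vaccine-related SAEs.

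- 80% chance of at least one: p = 1 − 0.20^(1/2000) = 0.0804%, or 1 in 1243. Stated: 0.08%, 1 in 1243.
- 50% chance: p = 1 − 0.50^(1/2000) = 0.0347%, or 1 in 2885.9. Stated: 0.03%, 1 in 2885.
- No events, 97.5% upper bound: 1 − 0.025^(1/2000) = 0.1843%, or 1 in 542.7. Stated: <0.18%, 1 in 542.

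All reproduce, apart from rounding.

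**3. Weight of one attribution.** Inputs: 2000 and 220 participants (Section 9.9.2) and the Miettinen-Nurminen interval (Section 9.6.2). The event counts are assumed, because the documents give none.

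Shift in the observed rate: 1/2000 = 0.05 points in V114 and 1/220 = 0.45 points in Prevnar 13.

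The limits are the values d that solve (p1 − p2 − d) / √{[r1(1 − r1)/2000 + r2(1 − r2)/220] × 2220/2219} = ±1.96. Here p1 and p2 are the observed rates, and r1 and r2 are the maximum-likelihood rates under r1 − r2 = d.

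The 0 vs 0 case can be done by hand. For the upper limit, r1 = d and r2 = 0, so d/(1 − d) = 3.8415/2000 × 2220/2219 = 0.001922 and d = 0.19 points. For the lower limit, |d|/(1 − |d|) = 3.8415/220 × 2220/2219 = 0.01747 and d = −1.72 points. The other cases were solved numerically.

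| Related SAEs, V114 vs Prevnar 13 | Difference (points) | 95% CI (points) |
|---|---|---|
| 0 vs 0 | 0.00 | −1.72 to 0.19 |
| 1 vs 0 | 0.05 | −1.67 to 0.28 |
| 0 vs 1 | −0.45 | −2.53 to −0.08 |
| 1 vs 1 | −0.40 | −2.48 to 0.01 |

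Of these four cases, zero is excluded only when the sole event is in Prevnar 13. If exactly one related SAE occurs and the vaccine has no influence on where it falls, that case has probability 220/2220 = 9.9%.

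**4. How many participants.** The documents give no emergency-unblinding rate. If it were 0.1% to 0.5% (assumption), 2220 × 0.001 = 2 to 2220 × 0.005 = 11 participants would have the code broken. Only those with an SAE whose relatedness is open to judgement would matter, and the documents do not allow that share to be estimated.

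**The case against.** The case against giving this much weight is strong, and most of it stands.

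- A reader might infer that the plan forces open-label attribution. It does not. The text allows a designee, and one who does not judge causality can comply in full. What remains is that nothing steers the task away from the causality assessor.
- A reader might infer that the protocol expressly requires the investigator to open the code after an outside physician has done so. That reach comes from sentence order alone.
- Controls already exist. Section 10.3.4 requires a causality assessment before the first SAE transmission, and Sections 8.4.1 and 8.4.4 set 24 hours for that report, so a blinded value may often exist. Section 10.1.9 requires traceable changes to source data, and 8.1.12 requires the date and circumstances of unblinding to be documented. Later changes can therefore be identified. But no rule says that they will be flagged or examined.
- Section 8.1.12 already permits the investigator to be unblinded for follow-up care. That permission rests on medical need. The IRT sentence is a requirement that rests on record-keeping.
- A reader might take the 0 vs 1 interval as proof that one judgement can decide the primary endpoint. It cannot. Section 9.6.2 classes vaccine-related SAE as Tier 2, without a p-value, and calls such intervals descriptive. Section 9.8 defines study success on OPA alone. The 0 vs 1 case is a selected one, and it applies an asymptotic interval to a single event.

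**Conclusion.** The point holds as a cheap improvement of low weight. Section 8.1.12 can unblind the causality assessor for an administrative reason, out of line with its own welfare-only rule and with Section 8.1.8. It provides no causality-before-disclosure step when someone else breaks the blind, and the analysis sections do not flag judgements made or changed after unblinding.

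The effect is confined to the reported interval for a rare, descriptive safety endpoint: 0.05 or 0.45 points per attribution, with a change in whether zero is included only in selected cases. The laboratory-based OPA lot-consistency hypothesis is unaffected. The conclusion assumes that the IRT step shows the assignment to whoever performs it and that it applies to outside code breaks. The documents suggest both but state neither outright. The event counts and the unblinding rate are illustrations, not estimates from the documents.

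**What to change.** **Section 8.1.12.** Have the IRT disposition update made by site staff who are already unblinded, a role that Section 6.3.3 provides, or by someone who does not assess causality for that participant. The update needs no participant contact, so it respects the contact ban in 6.3.3. Add that, when someone else broke the blind, the investigator records causality before learning the assignment where possible. Emergency access and the rule against delaying unblinding stay unchanged. Reconcile the section with Sections 7.1 and 8.1.8.

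**Section 9.6.2.** Flag any SAE causality assessment entered or changed after the assessor was unblinded. Report a sensitivity summary of vaccine-related SAEs using the last blinded assessment where one exists. The main analysis value need not be frozen at the blinded assessment, since later diagnostic information is legitimate. Do not count unassessed events as related: that would turn a plainly unrelated event into an endpoint event and add bias.

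**Cost.** A few sentences in the protocol, one IRT task for existing unblinded staff, and one data flag with a short summary. No additional participants, visits or staff.
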